Chang Gung Memorial Hospital

NCT00952718

Date: 2019/10/31

Study Protocol:

Patients aged 40–80 years from the outpatient clinic of the Department of Pulmonology of a tertiary care medical centre who had bronchiectasis were eligible. Bronchiectasis was confirmed by clinical history, such as coughing, shortness of breath and exertional dyspnoea, pulmonary function tests and high-resolution computed tomography.

Those who were using steroids (including inhalation or oral), had recent exacerbation within six weeks, poor consciousness level and cerebrovascular or neuromuscular disorders were excluded. The eligible subjects were then randomly divided into either inspiratory muscle training or control groups. All technicians who performed the different measurements and assessed the outcomes were blinded to group allocation, and all measurements were performed at the beginning and end of the eightweek programme. The pulmonary function tests were performed in a pulmonary functional laboratory using a standard spirometer (Vitalograph, Serial Spirotrac, Buckingham, USA) according to the American Thoracic Society recommendations, and the measurements included parameters of forced vital capacity (FVC), FEV1 and maximum mid-expiratory flow. The best FVC measurement was recorded along with FEV1 and FEV1/FVC calculations.

After pulmonary function parameters were recorded, the bronchodilator test was used to check if the participant had a hypersensitive airway. The reversibility of the airway obstruction was defined as a 15% or greater improvement in FEV1 and at least a 200 mL increase in FEV1. None of our eligible patients showed a positive bronchodilator response. All measurements are presented as percentage predicted value. Baseline characteristics including height, weight, body mass index and duration of the disease, and the resting oxyhaemoglobin saturation (SpO2), lowest resting SpO2, Borg Scale during a 6-minute walking test, MIP, maximal expiratory pressure (MEP),and St George's Respiratory Questionnaire (SGRQ) were obtained in the Department of Respiratory Therapy.

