SpO2 was measured using a finger pulse oximeter (FingerPrint, BCI International, Wisconsin,USA). Resting dyspnoea was quantified using the modified Borg Scale, which ranges from 0.5 to 10.27 The 6-minute walk work (6Mwork) value was calculated as body mass × distance covered during the 6-minute walking test. MEP was measured after maximal inspiration, while MIP was measured after maximal expiration with each subject seated and wearing a nose-clip. An experienced respiratory therapist strongly urged the subjects to make maximum

inspiratory and expiratory efforts at or near residual and total lung capacity, respectively.

Determinations were repeated until two technically satisfactory measurements were recorded, with the highest value used for calculations. St George's Respiratory Questionnaire has 76 items on symptoms (frequency and severity of respiratory symptoms), activity (activities caused or limited by breathlessness), and impact (social functioning and psychological disturbances resulting from airway disease) on daily life. The scores range from 0 to 100, with higher scores indicating poorer health. A mean change score of 4 units was defined as slightly efficacious treatment, 8 moderately efficacious, and 12 very effective treatment.

The inspiratory muscle training programme was started at an intensity of 30% MIP, and increased by 2 cmH2O each week. A pressure threshold device (Threshold IMT HS730, Resironics Inc, Cedar Grove, NJ, USA) was used. During training, patients were in a sitting position with a nose-clip and were instructed to place their lips around the mouthpiece, inhale with enough force to open the valve, exhale through the mouthpiece, and then continue inhaling and exhaling without removing the device from their mouths. Patients could take intermittent periods of rest if they felt uncomfortable. They were encouraged to perform inspiratory muscle training for 30 minutes per day, at least five days a week, for eight weeks. If the training sessions could not be completed due to increased resistance, the last part of the session was performed with the previous resistance setting.

Patients in the control group did not receive any training programme. Both groups were monitored by telephone call once or twice a week until the end of the study. The medication profiles were also recorded. No medication was altered during the study period.

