### **Statistical analysis**

Baseline characteristics were compared using the Student's t-test for continuous variables and Fisher's exact test for categorical variables.

Results are presented as absolute number (percentage) or mean (standard deviation) and adjusted for age by linear regression analysis.

The difference for each variable was compared with two-way repeated measures analysis of variance between the two groups and within each group. Paired sample T-tests were used for comparison within each group. A two-tailed P-value of less than 0.05 was considered significant. All statistical analyses were performed using the SPSS 14.0 software package (SPSS Inc., Chicago, IL, USA).

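### Every outcome is tested at an unadjusted two-sided 0.05 with no primary outcome: with 11 to 14 outcomes and assumed correlations of 0.7 to 0, a false between-group difference has a chance of about 22–51%, not 5%

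*Combined protocol and SAP*

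**What the plan says.** The inferential plan is in the Statistical analysis section. It states: "The difference for each variable was compared with two-way repeated measures analysis of variance between the two groups and within each group". It then adds: "Paired sample T-tests were used for comparison within each group". One threshold covers everything: "A two-tailed P-value of less than 0.05 was considered significant".

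The outcomes have to be gathered from the Study Protocol text. For spirometry, "the measurements included parameters of forced vital capacity (FVC), FEV1 and maximum mid-expiratory flow", and FEV1/FVC is also calculated. Resting and lowest oxygen saturation, the Borg score, maximal inspiratory and expiratory pressures (MIP, MEP), 6-minute walk work and the SGRQ complete the list. On timing, "all measurements were performed at the beginning and end of the eightweek programme". The SGRQ is described as covering symptoms, activity and impact, and "The scores range from 0 to 100, with higher scores indicating poorer health", but the text does not say which SGRQ scores are analysed.

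Neither section names a primary outcome, ranks the outcomes, gives a sample-size basis that would imply a primary, or adjusts for multiplicity. The SGRQ change bands of 4, 8 and 12 units grade the size of a benefit; they do not make the SGRQ primary. The text was written after the fact, as a results-type sentence shows: "None of our eligible patients showed a positive bronchodilator response".

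**The concern.** With a separate 0.05 test for every variable and nothing to say which one decides, a single nominally significant result in lung function, muscle strength, exercise, saturation, dyspnoea or quality of life can be presented as evidence that training works. The outcome that carries the claim can be chosen after the results are seen.

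Two further gaps widen the choice. A two-way repeated-measures ANOVA yields group, time and group-by-time terms, and the plan does not say which is the between-group test. The paired t-tests use the same threshold, and nothing bars a significant change in the trained group from being offered as efficacy. Such a test makes no comparison with control, so any change over time common to both groups would count as benefit.

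**Working it through.** The documents give no familywise error rate, so there is no such figure to reproduce. Their only error figure is the per-test two-sided 0.05, which is 0.025 in the direction of benefit.

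**Number of outcomes, k (counted from the Study Protocol text).** FVC, FEV1, FEV1/FVC and mid-expiratory flow (4); resting and lowest SpO2 (2); Borg (1); 6-minute walk work (1); MIP and MEP (2); SGRQ (1). Total: 4 + 2 + 1 + 1 + 2 + 1 = 11. Three SGRQ area scores in place of one give 13; adding a total score gives 14.

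**Assumptions.** No true effect on any outcome; one between-group test per outcome; a common correlation r between test statistics, each oriented so that positive favours training. The documents give no value for r, so a range is shown.

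**Independent outcomes (r = 0).**
- Either direction: 1 − 0.95^11 = 0.431; 1 − 0.95^14 = 0.512.
- Favouring training: 1 − 0.975^11 = 0.243; 1 − 0.975^14 = 0.298.

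**Correlated outcomes.** Write each statistic as √r·U + √(1−r)·e, with U shared and all terms standard normal, and let c = 1.96. Then
- either direction: 1 − ∫ [Φ((c − √r·u)/√(1−r)) − Φ((−c − √r·u)/√(1−r))]^k φ(u) du
- favouring training: 1 − ∫ [Φ((c − √r·u)/√(1−r))]^k φ(u) du

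| k, direction | r = 0 | 0.3 | 0.5 | 0.7 | 0.8 | 0.9 |
|---|---|---|---|---|---|---|
| 11, either | 0.431 | 0.375 | 0.304 | 0.223 | 0.180 | 0.131 |
| 11, favouring training | 0.243 | 0.191 | 0.152 | 0.112 | 0.090 | 0.066 |
| 14, either | 0.512 | 0.438 | 0.348 | 0.249 | 0.197 | 0.141 |
| 14, favouring training | 0.298 | 0.224 | 0.174 | 0.124 | 0.099 | 0.070 |

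Across k = 11 to 14 and r = 0.7 to 0, the ranges are therefore 22–51% and 11–30%. Simulated two-sample t-tests with 13 and 30 patients per group (assumed sizes) agree with the table to within about one percentage point.

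**Adding the paired t-tests.** Suppose a favourable paired test in the trained group also counts as a benefit. With no mean change in either group and equal group sizes, let zT and zC be the within-group statistics, so that the between-group statistic is (zT − zC)/√2. A false benefit is declared if either this or zT exceeds 1.96 on any outcome. In 200,000 simulated trials, for r = 0, 0.3, 0.5 and 0.7:
- k = 11: 0.372, 0.287, 0.231, 0.173
- k = 14: 0.450, 0.332, 0.262, 0.189

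The false-benefit chance is then about 17–37% with 11 outcomes and 19–45% with 14.

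**The case against.** The strongest reply is that the headline range rests on an inferred outcome family and a stylised null.

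- **The count.** Several measures appear in a sentence about baseline characteristics and become outcomes only because all measurements were repeated at eight weeks. The count could also be higher: testing 6-minute walk distance separately gives 12 to 15 outcomes and a range of 23–54%. With only 6 outcomes the chance is still 16–26% for r = 0.7 to 0.
- **The upper end.** Fourteen independent outcomes cannot occur, because an SGRQ total is built from its areas and FEV1/FVC from two other listed measures. Treating the SGRQ total as an equal-weight composite and leaving the rest independent lowers the figure only to about 50% (29% favouring training).
- **The lower end.** The range stops at r = 0.7. At r = 0.8 the figure is 18–20%, and at 0.9 it is 13–14%.
- **The null.** MIP is the capacity being trained, so no effect on it is the least plausible null. Dropping it leaves 10 to 13 outcomes and 21–49% (11–28% favouring training).
- **The record.** A primary outcome may be documented elsewhere; only these documents were available.
- **The remedy.** Prespecification cannot be restored in a retrospective text. Labelling every outcome exploratory, with confidence intervals, is a defensible alternative to Holm.

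These points show that the figures depend on assumptions and that zero correlation is a bound. None supplies the missing rule, and every variant stays above twice the nominal 5%. The exploratory label would also serve, but only if the significance threshold and any efficacy claim resting on it were dropped.

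**Conclusion.** The concern holds. Followed as written, the plan leaves the overall false-positive rate uncontrolled. Under a global null the chance of a false between-group difference is about 22–51%, and of one favouring training about 11–30%, instead of 5% and 2.5%. The size depends on the assumed 11 to 14 outcomes and common correlation of 0.7 to 0; the conclusion does not. The absence of a primary outcome is a finding about these documents only. This needs correcting before any efficacy claim is rested on the P-values.

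**What to change.** Replace the single-threshold sentence with a rule that does the following.

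1. Lists the outcome family, including which SGRQ scores belong to it.
2. Takes the group-by-time contrast as the between-group test for each outcome, and states whether that test is age-adjusted, since the section also mentions age adjustment by linear regression.
3. Applies Holm's procedure across the listed family at two-sided 0.05. The first step is 0.05/11 = 0.0045 with 11 outcomes or 0.05/14 = 0.0036 with 14. Holm is valid under any correlation, so none of the assumed r values is needed.
4. If, and only if, a primary outcome was documented before the data were seen, tests that one at two-sided 0.05 and reports the others under Holm or as exploratory estimates with 95% confidence intervals. A primary should not be newly chosen now.
5. States that the within-group paired t-tests are descriptive and do not support an efficacy claim.

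The cost is a rewritten paragraph and a re-reading of existing P-values; no new data are needed. The two-way repeated-measures ANOVA already produces the group-by-time term, but if the reported P-values came from another term, or from an age-adjusted model, the relevant ones must be extracted or re-run. Some results with P between about 0.004 and 0.05 could no longer be called significant, and results already reported may need relabelling.
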